8.3.7. The percent change of granulation tissue (%) relative to baseline

This exploratory endpoint is defined as the percent difference of viable granulation tissue between Day X and baseline:

$$\Delta pctGra = GranulationX - Granulation0$$

where,

Granulation0 = percent of granulation tissue (%) at baseline as assessed by independent assessor

GranulationX = percent of granulation tissue (%) at Day X (e.g. Day 6-9) upon final dressing removal as assessed by independent assessor.

The following hypothesis will be tested:

Null: $\Delta pctGra_{VFCC} - \Delta pctGra_{Control} = 0$
 $\neq 0$

Alternative: $\Delta pctGra_{VFCC} - \Delta pctGra_{Control}$

where $\Delta\text{pctGra}_{\text{VFCC}} - \Delta\text{pctGra}_{\text{Control}}$ is the percent difference of granulation tissue from baseline to Day X upon final dressing removal between the VFCC with NPWTi-d group and Control group.

The appropriate generalized linear modeling will be used to analyze the endpoint with potential fixed effects: clinical site; baseline total wound area; body mass index [BMI]; treatment arm and indicator of baseline wound undermining. If any of the covariates (except treatment arm and site ID) is not statistically significant at the 0.1 level, then the non-significant term(s) will be removed from the model and the updated model will be re-run. These endpoints will be summarized based on the ITT (with no imputation) analysis sets.

8.3.8. The absolute change of area covered with granulation tissue (cm²) relative to baseline

This exploratory endpoint is defined as the difference in the absolute value of viable granulation tissue between Day X and baseline, where the absolute value of viable granulation tissue is the percent of viable granulation tissue divided by 100 and multiplied by total wound area:

$$\Delta\text{absGra} = \frac{\text{AreaX} \times \text{GranulationX} - \text{Area0} \times \text{Granulation0}}{100}$$

where,

Area0 = the total wound area at baseline

AreaX = the total wound area at Day X (e.g. Day 6-9) upon final dressing removal.

Granulation0 = percent of granulation tissue (%) at baseline as assessed by independent assessor

GranulationX = percent of granulation tissue (%) at Day X (e.g. Day 6-9) upon final dressing removal as assessed by independent assessor.

The following hypothesis will be tested:

Null: $\Delta\text{absGra}_{\text{VFCC}} - \Delta\text{absGra}_{\text{Control}} = 0$

Alternative: $\Delta\text{absGra}_{\text{VFCC}} - \Delta\text{absGra}_{\text{Control}} \neq 0$

where $\Delta\text{absGra}_{\text{VFCC}} - \Delta\text{absGra}_{\text{Control}}$ is the difference of the absolute value of granulation tissue from baseline to Day X upon final dressing removal between the VFCC with NPWTi-d group and Control group.

The appropriate generalized linear modeling will be used to analyze the endpoint with potential fixed effects: clinical site; baseline total wound area; body mass index [BMI]; treatment arm and indicator of baseline wound undermining. If any of the covariates (except treatment arm and site ID) is not statistically significant at the 0.1 level, then the non-significant term(s) will be removed from the model and the updated model will be re-run. These endpoints will be summarized based on the ITT (with no imputation) analysis set.

8.3.9. Treatment Application Characteristics

The endpoints below will be summarized as appropriate in reference to Section 7.1 in either the VFCC with NPWTi-d group or Control group based on the Safety analysis sets.

Total number of collagenase ointment tubes used per Subject, summarized as the number of all new tubes used for each Subject by visit and the total new tubes used from baseline to Day 6-9 upon dressing removal.

Other treatment application characteristics, such as system leaks and additional drapes used in the VFCC with NPWTi-d group and tube size, SOC dressing type, and whether the dressing contains an antimicrobial or cleanser in the Control group.

Number of blockage and leak alarms (obtained from the V.A.C.ULTA™ Therapy Unit log), summarized as the number of all blockage and leak alarms recorded in the V.A.C.ULTA™ Therapy Unit log for each Subject by visit and the total number of blockage and leak alarms from baseline to Day 6-9 upon dressing removal.

The endpoints below will be listed in the VFCC with NPWTi-d group based on the Safety analysis set:

- # of System Fault Alarms per patient (overall and per day)
- # of Battery Critical Alarms per patient (overall and per day)
- # of V.A.C. VeraFloTM Blockage Alerts per patient (overall and per day)
- # of V.A.C. VeraFloTM Low Pressure Alarms per patient (overall and per day)
- # of V.A.C. VeraFloTM Therapy Blockage Alarm – Therapy Interrupted per patient (overall and per day)
- #V.A.C. VeraFloTM Low Pressure Alarms/#V.A.C. VeraFloTM Blockage Alerts % per patient (overall and per day): this is the percentage of time initial alert was not managed appropriately and turned into an alarm
- #V.A.C. VeraFloTM Therapy Blockage Alarm – Therapy Interrupted/#V.A.C. VeraFloTM Blockage Alerts % per patient (overall and per day): this is the percentage of time initial alert was not managed appropriately and turned into a therapy interrupted alarm
- # of V.A.C. VeraFloTM Leak Alarms per patient (overall and per day)
- # of V.A.C. VeraFloTM Leak Alarm – Therapy Interrupted per patient (overall and per day)
- #V.A.C. VeraFloTM Leak Alarm – Therapy Interrupted/#V.A.C. VeraFloTM Leak Alarms % per patient (overall and per day): this is the percentage of time initial alarm was not managed appropriately and turned into a therapy interrupted alarm
- # of VeraFloTM Therapy Blockage Alert's per patient (overall and per day)

The exploratory endpoints below will be summarized and compared between the VFCC with NPWTi-d group and Control group based on the Safety analysis sets using the Wilcoxon Rank-sum test.

- Total time to perform treatment applications and/or dressing changes per Subject, defined as the difference between start time and end time for treatment application or dressing change.

9. SAFETY ANALYSIS

9.1. Laboratory Tests

Pregnancy test results will be presented in listings only.

9.2. Adverse Events

All treatment-emergent adverse events (TEAEs), which are defined as adverse events with onset or worsening of pre-existing conditions on or after the initial dressing application through the course of the study, will be summarized. The number and percentage of treated Subjects who experienced at least one adverse event in each system organ class by preferred term will be summarized. In any given category (e.g., system organ class or preferred term), a Subject will be counted only once. The denominator for the calculation of percentages will be the number of Subjects in the Safety analysis set. The test for significant between-treatment differences will be carried out using the Fisher's exact test.

The following summary tables and listings will be presented by treatment arm:

- Overview of all treatment-emergent adverse events (TEAEs)
- Incidence of all treatment-emergent adverse events (TEAEs) by system organ class and preferred term
- Incidence of all treatment-emergent adverse events (TEAEs) by system organ class, preferred term, and maximum severity
- Incidence of all serious adverse events (SAEs) by system organ class and preferred term
- Incidence of treatment-related TEAEs by system organ class and preferred term
- Incidence of treatment-related TEAEs by system organ class, preferred term, and maximum severity
- Incidence of treatment-related serious adverse events (SAEs) by system organ class and preferred term
- Incidence of most common >5% TEAEs in any one treatment group by preferred term only
- Listing of all treatment-related adverse events
- Listing of all treatment-related serious adverse events (SAEs)
- Listing of discontinuations: Subjects who discontinued from the study due to any adverse event
- Listing of deaths: Subjects who died of any cause during the study

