### **8.3.7. Analysis of Safety Endpoint**

All safety results will be presented based on the Safety Analysis Set. All TEAEs will be summarized by treatment arm. Subject incidence of TEAEs will be summarized by treatment arm and by MedDRA system organ class and preferred term. For each coded medical term, the proportion of Subjects who experience at least one treatment-emergent:

- adverse event(s);
- adverse event(s) related to treatment
- serious adverse event(s);
- serious adverse event(s) related to treatment
- adverse event(s) by severity (mild, moderate, severe);
- adverse event(s) leading to treatment/study discontinuation, or
- serious adverse event(s) leading to treatment/study discontinuation will be reported.

A listing of death(s), Subjects who died of any cause during the study, will be presented.

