4.2. Safety Endpoint(s)

The safety endpoint for this study is the incidence of adverse event(s) (AEs). All AEs will be coded using the MedDRA coding dictionary version 22.0 or higher.

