5.1. Safety Population

Safety Analysis Set includes all randomized Subjects who received either VFCC and NPWTi-d or collagenase ointment for any length of time. Subjects will be analyzed as treated.

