6. GENERAL STATISTICAL CONSIDERATIONS

- Data processing, tabulation of descriptive statistics and calculation of inferential statistics will be performed primarily using SAS version 9.4 or higher (SAS Institute, Cary, NC). If the use of other software is warranted, the final report will detail software deployed along with the reasons for use.
- Summaries of continuous variables will show the number of non-missing values [n], along with the mean, standard deviation, median, minimum, and maximum. In general, minimum and maximum values will be presented to the same precision as the raw data; the mean and median will be presented to one decimal place more than the raw data. Standard deviation

and confidence interval limits will be presented to two decimal places more than the raw data.

- Summaries of categorical (qualitative) variables will include the frequency and percentage of Subjects in each category. In general, the denominator for the percentage calculation will be based upon the total number of Subjects in the study population, unless otherwise specified. Percentages will be presented to 1 decimal place, except a value of zero, which will only be displayed as “0” or unless otherwise specified.
- Subjects in all the analysis sets will be summarized by treatment arm and overall.
- P-values will be presented to four decimal places. A p-value less than 0.0001 will be presented as < 0.0001 or < .0001.
- The assessment prior to the initial treatment application will be considered a baseline value. If debridement is deemed to be necessary, then the assessment directly after debridement will be used as the baseline reference.
- Percent change from baseline will be calculated using the relevant post initial dressing application value minus the baseline value.

Other ad hoc data analyses may be conducted to characterize the activity of the treatment. These additional ad hoc analyses will be decided at the time of the analysis and will be identified in the output and CSR. Other ad hoc data analyses to characterize safety and/or efficacy activity of treatment arms may be conducted. These additional ad hoc analyses will be decided at the time of analysis and will be labeled as such. Due to the exploratory nature of the analyses, no adjustment for multiplicity will be made in these ad hoc analyses.

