6.2. Determination of Sample Size

The study will randomize approximately 60 Subjects from approximately 15 sites in a 1:1 ratio to either the V.A.C. VERAFL0 CLEANSE CHOICE™ (i.e., Treatment) arm or the collagenase ointment (i.e., Control) arm. Sample size determination is based on the primary endpoint. It was estimated that slough reduced by almost 20% in the Tender Wet 24 group and 10% in the Iruxol N group in M. Konig et al.¹ Assuming a 20% increase in clean, healthy, viable wound bed surface area in the collagenase ointment group and a 40% increase in clean, healthy, viable wound bed surface area in the VFCC and NPWTi-d group, and a typical standard deviation of 22%, 23

evaluable Subjects per group would provide approximately 80% power to detect a statistically significant difference using the Wilcoxon Rank-Sum test (nQuery Advisor® 7.0).

In some circumstances, even though the investigator assessed the wound to have $\leq 2/3$ area of clean, healthy, and viable wound bed, it may not meet the requirement when assessed by the independent assessor if measured by a 3D camera. Such Subjects will be excluded from the mITT for the analysis of the primary endpoint. To allow for this possibility, plus the possibility that some Subjects may be lost to follow-up prior to their post-baseline assessment at the Day 6-9 visit, the sample size is increased to a total of 60 randomized Subjects (i.e., 30 Subjects per arm). This accounts for an approximately 23% drop out rate.

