1	Section 8.1 Primary Efficacy Analysis. Added the option to pursue a proportional odds model if appropriate.	Accounts for the possible situation of severe violation of the normality assumption in the final linear model for the primary analysis.
1	
Section 8.2 Secondary Efficacy Analysis and Section 8.3 Exploratory Analysis.
 
Identified 12 relevant secondary analyses of interest: three (3) within-treatment testing for the VFCC arm only and nine (9) between treatment arm testings. Outlined a Holm method of multiplicity adjustments in these secondary testing.
 
Changed formulas for percent change in area, percent change in volume, percent change in granulation, absolute change in area, absolute change in volume and absolute change in granulation to be consistent with primary endpoint definition such that negative values represent reductions and positive values increases with the passage of time.
 
Added six (6) within-VFCC tests and nine (9) within-Collagenase tests as exploratory analyses.
 
Modified statistical test used for categorical data analysis to Fisher's exact test rather than Chi-square or Fisher's exact test (if the sample size in any subgroup is less than 5).
	To add important clarifying details
1	Section 8.3.6 and 8.3.7. Clarified the percent granulation tissue in formula is based on the percent viable granulation tissue derived from the tissue typing work done by the independent assessor from the wound images.	Clarified input variable in the formulas with percent granulation tissue.
1	Sections 9.2 and 9.3. Added statements in both sections to describe the statistical test (namely, Fisher's Exact test) to be carried out for between-treatment differences in the adverse event and medication summaries.	Specify the appropriate test for differences.

Statistical Analysis Plan

CLIN-PROT-SAP-05-830770

Version: 1

Status: Release

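### The safety endpoint is compared between arms by a Fisher's exact p-value alone; with no risk difference or confidence interval, the output will not show how large an excess of adverse events the data leave open

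*SAP*

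**What the plan says.** SAP 4.2 and Protocol 3.5 name one safety endpoint, the incidence of adverse events. Protocol 8.3.7 planned description only: "All TEAEs will be summarized by treatment arm", and "Subject incidence of TEAEs will be summarized by treatment arm and by MedDRA system organ class and preferred term".

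SAP 9.2 keeps those tables, with the Safety Analysis Set as denominator, and then states: "The test for significant between-treatment differences will be carried out using the Fisher's exact test". The revision history in SAP Section 12 records this as an addition, a test "to be carried out for between-treatment differences in the adverse event and medication summaries". SAP 9.2 gives no alpha, sidedness, effect measure, interval or margin, and no rule for reading a non-significant result.

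The general conventions in SAP Section 6 mention that "confidence interval limits will be presented to two decimal places more than the raw data". That is a rounding rule within the bullet on continuous variables; it does not plan an interval for adverse event incidence.

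On numbers, SAP 5.1 says: "Safety Analysis Set includes all randomized Subjects who received either VFCC and NPWTi-d or collagenase ointment for any length of time". SAP 6.2 sets 60 randomized subjects, 30 per arm, on the basis of the primary efficacy endpoint. The safety comparison therefore has at most about 30 per arm.

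**The concern.** The SAP went beyond the protocol's descriptive plan, but only as far as a p-value. A p-value does not say how much excess harm remains compatible with the data, and at this sample size that is the useful safety question. The efficacy side is treated differently: the model code in SAP 8.1 asks for the difference in least-squares means with confidence limits. Efficacy gets an estimate with its uncertainty, while safety gets counts, percentages and a test.

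Two things are at stake. A large true excess of adverse events would usually come out as non-significant. And a result with no difference between arms would carry no indication of how wide the remaining uncertainty is.

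**Working it through.** **Inputs from the documents.** 60 randomized 1:1, so 30 per arm (SAP 6.2). Safety set: randomized and treated (SAP 5.1). Method: Fisher's exact test (SAP 9.2).

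**Assumptions.** Two-sided alpha 0.05, all 30 per arm treated, control event rate varied from 0% to 70%, true excess 20 points. The documents state no adverse event rates.

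**1. The plan's own figure.** There is no power or precision figure for safety. The only one concerns the primary endpoint: 23 evaluable per group for about 80% power (20% vs 40%, SD 22%, Wilcoxon). Noether's formula is n = (z0.975 + z0.80)² / [6(p - 0.5)²], with p = Φ(20 / (22√2)) = 0.740. This gives n = 7.849 / (6 × 0.2398²) = 22.7, so 23 per group. From 46 evaluable to 60 randomized is a loss of 14/60 = 23%. The figure reproduces, and nothing in it addresses adverse events.

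**2. Chance that Fisher's test misses a 20-point excess.** All 31 × 31 pairs of counts were enumerated, each weighted by its two binomial probabilities, and those with p ≤ 0.05 were summed. The miss probability is one minus that sum.

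| Control | VFCC | Missed |
|---|---|---|
| 0% | 20% | 43% |
| 5% | 25% | 56% |
| 10% | 30% | 63% |
| 20% | 40% | 70% |
| 30% | 50% | 74% |
| 40% | 60% | 74% |
| 50% | 70% | 74% |
| 60% | 80% | 70% |
| 70% | 90% | 63% |

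A 10-point excess is missed 90% (10% vs 20%) to 93% (0% vs 10%) of the time. If the trial stopped at the interim look, with about 15 per arm, a 20-point excess would be missed 85-90% of the time at control rates of 10-70%.

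**3. What an interval adds.** Newcombe's interval combines the Wilson limits (l, u) of the two proportions:
- lower = d - √[(p1 - l1)² + (u2 - p2)²]
- upper = d + √[(u1 - p1)² + (p2 - l2)²]

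*3/30 vs 3/30.* Wilson limits are 0.035 and 0.256 in each arm, so the half-width is √(0.065² + 0.156²) = 0.169. Fisher p = 1.0; the 95% CI is -17 to +17 points.

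*5/30 vs 0/30.* Wilson limits are 0.073 to 0.336 and 0 to 0.114. Lower = 0.167 - √(0.093² + 0.114²) = 0.020; upper = 0.167 + √(0.169² + 0²) = 0.336. Fisher p = 2 × C(30,5)/C(60,5) = 0.052; the 95% CI is +2 to +34 points.

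*Other non-significant results.* 10/30 vs 3/30 gives p = 0.057 and a CI of +2 to +42. 20/30 vs 12/30 gives p = 0.069 and a CI of +2 to +48.

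**The case against.** The strongest reply is that this is a reporting refinement. SAP 9.2 requires numbers and percentages by arm for all TEAEs, by maximum severity, for SAEs and for treatment-related events, with listings of deaths and of discontinuations due to adverse events. From those counts any reader can work out a risk difference and its interval. That stands in part: Fisher's test is the only *inferential* comparison, not the only information. But percentages give a point difference without its uncertainty, and the SAP itself chose to go beyond description.

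A second reply is that the limitation is mainly one of sample size. That also stands. Judged only by whether it excludes zero, the Newcombe interval still misses a 20-point excess 51-65% of the time at control rates of 10-70%. Part of its apparent advantage is that it is approximate while Fisher's test is conservative; in the 5/30 vs 0/30 example the two disagree at the 5% level. The interval's value lies in displaying the uncertainty, not in adding power.

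A reader might infer that a non-significant result is meant to be read as comparable safety. The documents do not support this: they contain no safety hypothesis, no margin and no comparable-safety claim. A reader might also infer that the device-specific risks in Protocol Table 2 are too rare for the test ever to detect. That table gives no frequencies, so the documents cannot settle it.

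**Conclusion.** The concern holds as a gap in reporting. Fisher's exact test is the only inferential between-arm comparison of the single safety endpoint, and no planned output shows how large an excess of adverse events remains open. At 30 per arm and two-sided 0.05, a true 20-point excess is missed 63-74% of the time at control rates of 10-70%. At rates of 0-5% the miss is lower, 43-56%. These figures rest on assumed event rates and on all 30 per arm being treated.

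The point does not touch the primary result, does not show that the sponsor intends a comparable-safety claim, and does not call for a larger trial. It is a cheap improvement.

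**What to change.** Add to SAP 9.2:

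> For any TEAE, treatment-related TEAE, SAE, treatment-related SAE and TEAE leading to discontinuation, the risk difference (VFCC minus control) will be reported with a two-sided 95% confidence interval (Newcombe or Miettinen-Nurminen, one method fixed in advance). Fisher p-values, if shown, are descriptive and unadjusted, and a non-significant result will not be taken as evidence of comparable safety.

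Fisher's test need not be deleted, and no safety margin needs to be invented; the defect is only the missing estimate with its interval.

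The cost is one SAP paragraph and a few lines of code, with no new data, no new subjects and no change in sample size. The downside is that the intervals will be wide and can disagree with Fisher's test near 0.05, so the safety statement becomes less favourable. Fixing the interval method before database lock removes the choice between methods once results are known.

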9.3. Other Safety Variables

Concomitant medications/therapies are defined as medications taken from the time of treatment application (Day 0 through the final visit). The WHO Drug Dictionary released MAR2019 or later will be used for the coding of medications.

The number of Subjects using concomitant medications will be summarized using the pharmacological subgroup name (ATC3) and preferred drug name based on the WHO Drug medical coding dictionary. In any given category (e.g., ATC3 or preferred drug name), a Subject will be counted only once. All Subjects in the Safety analysis set will be accounted for in the summation. Listings for concomitant medications will be presented by Subject. The test for significant between-treatment differences will be carried out using the Fisher's exact test.

10. CHANGES FROM PLANNED ANALYSIS

In Section 8.3.5.3 of the study protocol, it states that, if appropriate, supportive/exploratory analyses of the secondary endpoint “Physician assessment of the need for debridement” may include:

- repeat the analysis above on the ITT and Per protocol analysis sets
- analyses comparing the treatment groups considering covariates (e.g., age, BMI, race/ethnicity, sex, wound undermining, and co-morbidities) and subsets of the data
- analyses comparing the heterogeneity of the treatment groups across clinical sites.

In Section 8.2.5 of this SAP, it states that “if appropriate, the analysis above will be repeated on the ITT (without imputation) and Per-Protocol analysis sets as supportive/exploratory analyses of this secondary endpoint.” as the other two analyses are expected to have minimal difference between the two treatment groups therefore are at risk for being deemed unnecessary and being removed.

Added other secondary and exploratory endpoints with corresponding analyses. See Section 12 Revision History for details on changes from previously planned analyses.

